5.1.2. Secondary effectiveness endpoint and secondary analyses

Secondary effectiveness endpoints are the incidence of "cardiogenic cerebral embolism" or "ischemic stroke" during the follow-up period in NVAF patients treated with warfarin or apixaban.

For each secondary endpoint, like the primary analysis, incidence of the secondary endpoint, Kaplan Meier curves and Hazard ratios with 95% confident intervals will be calculated

5.2. SAFETY ENDPOINTS

5.2.1. Primary safety endpoint and primary analyses

Primary safety endpoint is incidence of major bleeding, which is defined as any bleeding requiring hospitalization.

1. Incidence of Major bleeding (per 1,000 person-year)

PFIZER CONFIDENTIAL

Page 11 of 51

- Survival curves of major bleeding-free patients (Kaplan-Meier curves) will be drawn for apixaban and warfarin cohorts. Difference in the two curves will be evaluated by a Logrank test.
- Risk of major bleeding in each cohort will be compared between balanced warfarin and balanced apixaban cohorts by using Cox proportional hazard analysis. Hazard ratio with 95% confident intervals will be calculated.

5.2.2. Secondary safety endpoint and secondary analyses

Secondary safety endpoints are the incidence of "intracranial hemorrhage", "gastrointestinal bleeding" or "intraocular bleeding" during the follow-up period in NVAF patients treated with warfarin or apixaban.

For each secondary endpoint ("intracranial hemorrhage", "gastrointestinal bleeding" or "intraocular bleeding"), like the primary analysis, incidence of each secondary endpoint, Kaplan-Meier curves and Hazard ratios with 95% confident intervals will be calculated

5.3. OTHER ENDPOINTS

None

5.4. COVARIATES

Items	definitions	roles
Gender	Male or female	Patient characteristics
		CCI
Body weight	≥ 60 kg or < 60 kg	Patient characteristics
eGFR (continuous)	Value in the baseline If a patient has multiple eGFR values, the values closest to the index date will be adopted	Patient characteristics
eGFR (categorical)	≥ 50 ml/min or < 50 ml/min	Patient characteristics
Serum creatinine (continuous)	Value in the baseline If a patient has multiple eGFR values, the values closest to the index date will be adopted	Patient characteristics

PFIZER CONFIDENTIAL

Serum creatinine (categorical)	≥ 1.5mg/mL or < 1.5	Patient
	mg/mL	characteristics
CHADS2	CHADS2 score will be calculated based on age and the presence of congestive heart failure, hypertension, diabetes, and stroke or TIA.	Patient characteristics
CHA2DS2-VASc	CHA2DS2-VASc score will be calculated based on age and the presence of congestive heart failure, hypertension, diabetes, stroke or TIA, vascular disease and sex category.	Patient characteristics
CCI		

Page 13 of 51

	CCI	
Medications		
CCI		
Treated with antiplatelet drug in baseline	Defined using prespecified drug- specific codes: Yes or No	Patient characteristics
PFIZER CO	NFIDENTIAL	

Page 14 of 51

		I
Treated with NSAIDs in baseline	Defined using prespecified drug- specific codes: Yes or No	Patient characteristics
Treated with gastric secretion inhibitor in baseline	Defined using prespecified drug- specific codes: Yes or No	Patient characteristics
Treated with statin-based drug in baseline	Defined using prespecified drug- specific codes: Yes or No	Patient characteristics
Treated with anti-hypertensives in baseline	Defined using prespecified drug- specific codes: Yes or No	Patient characteristics
Treated with anti-arrhythmics in baseline	Defined using prespecified drug- specific codes: Yes or No	Patient characteristics
Treated with beta-blockers in baseline	Defined using prespecified drug- specific codes: Yes or No	Patient characteristics
Procedures		
Cardioversion	Defined using prespecified medical procedure codes: Yes or No	Patient characteristics
Cardiac ablation	Defined using prespecified medical procedure codes: Yes or No	Patient characteristics
Anticogulation		
INR (warfarin cohort)	Continuous variable. * Only available for patients treated with warfarin	Patient characteristics
Apixaban doses	2.5 mg BID or 5mg BID * Only available for patients treated with apixaban	Patient characteristics

Chronically prescribed medicines

Medicines that had been prescribed at least for 30 days during the baseline period.

PFIZER CONFIDENTIAL

6. HANDLING OF MISSING VALUES

No imputation for missing values will be conducted.

7. STATISTICAL METHODOLOGY AND STATISTICAL ANALYSES

7.1. STATISTICAL METHODS

7.1.1. Patient characteristics

Means with standard deviations or medians with quartile values (25% and 75% values) will be provided for continuous variables when performing descriptive analysis of continuous data. Numbers and percentages will be provided for dichotomous and polychotomous variables when performing descriptive analysis of categorical data. Bivariate comparisons of baseline characteristics and outcomes measures will be provided. Appropriate tests (unpaired t-test or Mann-Whitney U-test, categorical variables: Chi-square or Fisher's exact test) will be used based on the distribution of the measure.

7.1.2. Patient characteristics balancing

In this study, cohorts with balanced patient characteristics (s-IPTW warfarin cohort and s-IPTW apixaban cohort) will be created from raw cohorts (raw warfarin and raw apixaban cohorts). A propensity score will be calculated based on multivariable logistic regressions in order to account for confounding effects and to ensure that patient characteristics will be balanced between the warfarin cohort and apixaban cohort. An inverse probability of treatment weighting (IPTW) method using the calculated propensity score will be applied. To avoid sample size inflation and to ensure appropriate estimation of variances, s-IPTW (stabilized IPTW) will be used here.

7.1.2.1. Calculation of propensity score

Propensity scores will be estimated by calendar year of index date based on multivariable logistic regression analyses that incorporate potential predictors of therapy as independent variables in the regression and cohort status (prescription of warfarin or apixaban) as the outcome. Consecutive calendar years of index dates may be collapsed to build logistic regression model with robustness. The following covariates will be included in the logistic regression:

- age on index date
- age at NVAF diagnosis
- gender

PFIZER CONFIDENTIAL

- CHADS₂ score in baseline
- CHA₂DS₂-VASc score in baseline
- heart failure diagnosis in baseline
- coronary heart disease diagnosis in baseline
- peripheral arterial disorder diagnosis in baseline
- myocardial infarction diagnosis in baseline
- hyperthyroidism or thyrotoxicosis in baseline
- TIA diagnosis in baseline
- stroke or SE diagnosis in baseline
- renal dysfunction diagnosis in baseline
- liver dysfunction diagnosis in baseline
- bleeding diagnosis in baseline
- hypertension diagnosis in baseline
- diabetes mellitus diagnosis in baseline
- treated with antiplatelet drug in baseline
- treated with NSAIDs in baseline
- treated with gastric secretion inhibitor in baseline
- treated with statin-based drug in baseline
- treated with anti-hypertensives in baseline
- treated with anti-arrhythmics in baseline
- treated with beta-blockers in baseline
- treated with heparins in baseline
- cardioversion in baseline

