1. AMENDMENTS FROM PREVIOUS VERSION(S)

From version 1.0 to version 1.1, no substantial changes have been made and only asministrative changes including correction of typos as follows; 1) in CCI

2) in 7.2.4 Summary of analysis, "time course of proportion of stroke-free" was changed to "time course of proportion of stroke/SE-free". Both changes are considered to be just administrative ones and little impact on the results would be expected.

From version 1.1 to version 2.0, two major changes have been made. Firstly, patient registration period descried in the section 2.1.1 was changed from "2008 to 2021" to "February 26, 2013 to December 31, 2021" to consider the launch date of apixaban in Japan. This change will make concurrent active control (i.e., warfarin cohort) for apixaban cohort. Secondly, calculation of propensity score was modified in the section "7.1.2.1" to adjust effect of time on treament selection (i.e., warfarin or apixaban). Propensity scores will be calculated by calendar year of index date.

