2.1.1. Study population

Patients registered in the MDV database from February 26, 2013 to December 31, 2021 will be used. First, patients with a NVAF diagnosis and received apixaban or warfarin as an anticoagulant after the NVAF diagnosis will be identified and then among them only patients who are 80 or older when they initiated these medications.

Based on the first anticoagulant prescribed, eligible patients will be allocated to one of two cohorts, an apixaban or warfarin cohort. Comparison will be made between these cohorts after balancing of the patient characteristics by a IPTW with stabilized weights (s-IPTW) method.

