4.5. SAMPLE SIZE CALCULATION

This study is a retrospective analysis of the structured data in the database and all eligible patients will be used for analysis.

The results of the feasibility assessment are shown below,

Table 1. The number of patients

Patient group	Number of patients
Patients diagnosed with NVAF at 80 years or an age older than 80 and data when patients are 80 or older are available.	
Treated with apixaban	76,260
Treated with warfarin	62,453

PFIZER CONFIDENTIAL

Page 9 of 51

Note that not all of these patients are eligible for this study because no inclusion and exclusion criteria were applied when the number of patients was estimated.

In the previous study (CER3)[2], incidence rate of major bleeding and stroke/SE were 2.5% for warfarin and 1.18 % for apixaban and 1.92% for warfarin and 0.98% for apixaban, respectively. Hazard ratios for major bleeding and stroke/SE were 0.58 and 0.57, respectively. In CER3 subgroup analysis on age, hazard ratios in sub-cohort of ages ≥ 80 years were 0.59 and 0.53 for major bleeding and stroke/SE, respectively. Although populations used for analysis are different (in the CER3 study, warfarin and apixaban could be started at any age, whereas in this study, the starting date for warfarin and apixaban was restricted to ages 80 years and older), difference may not be very large because the mean age of populations in CER3 is around 77 years old in both warfarin and apixaban cohorts. Sample size calculation was performed based on the CER3 results of older age subgroup analysis.

	Assumption: Values used for calculation	Calculated results
For major bleeding		
Type I error rate	0.05	
Type II error rate	0.2	
Hazard ratio	0.59	
N ratio in apixaban and warfarin cohorts	1:1	
Event rate for warfarin	2.5%/year	
Event rate for apixaban	1.18%/year	
Total events needed		113
Estimated number of patients		6,141
For Stroke/SE		
Type I error rate	0.05	
Type II error rate	0.2	
Hazard ratio	0.53	
N ratio in apixaban and warfarin cohorts	1:1	
Event rate for warfarin	1.92%/year	
Event rate for apixaban	0.98%/year	
Total events needed		78
Estimated number of patients		5,379

Table 2. Sample size calculation

Even allowing for the fact that 1) event rate may be higher because only patients whose index date is at 80 years or older (that is, high risk population for both stroke/SE and major PFIZER CONFIDENTIAL

Page 10 of 51

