7.1.2.2. IPTW with stabilized weights[6]

IPTW with stabilized weights will be used to balance patient characteristics between two groups using propensity score calculated by using a multivariable logistic model as mentioned above (see above 7.1.2.1). However, if a treated patient has a very low propensity score, a very large weight can be created. Large weights can increase the variability of estimated treatment effect. In order to address this, the weights can be stabilized. Stabilized weights will be calculated by using a formula shown below, by multiplying the treatment and control weights by a constant, equal to the expected value of being in the treatment or comparison cohorts, respectively.

 $W_i = \frac{Z}{PS_i} + \frac{1-Z}{1-PS_i}$, z: probability of treatment without considering covariates PFIZER CONFIDENTIAL

The distribution of the stabilized weight will be reviewed. If there are extreme outliers, the large weights could be set to a less extreme value (e.g. recoding all weights that are outside 5th and 95th percentile). If needed, truncation can be done after stabilizing the weights. After the weights are applied, the balance of the baseline covariates will be assessed. First, the means and proportions of baseline variables are compared. The standardized difference compares the difference in means in units of the standard deviation. If the standardized difference is less than 10%, the covariates are considered balanced.

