7.1.2.5. Calculation of hazard ratio with 95% confident intervals

Cox proportional hazards model will be used to compare endpoints in each of the sIPTW cohorts, with robust sandwich estimates to account for the clustering within balanced sets. The Cox proportional hazards model will include only index OAC treatment (apixaban or warfarin) as the independent variable if patient characteristics are well balanced between groups based on standardized difference in components of the PS. If not balanced, the unbalanced variable will be also included to the model in addition to the index OAC treatment. The hazard ratios with corresponding 95% confidence intervals and p-values will be reported.

PFIZER CONFIDENTIAL

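### If index years are collapsed, calendar time is unadjusted within each block, and the add-if-unbalanced Cox rule does not cover index year

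*SAP*

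**What the plan says.** SAP section 1 lists the by-year PS as one of two major changes in version 2.0, made "to adjust effect of time on treament selection (i.e., warfarin or apixaban"). The other change resets the study period "to consider the launch date of apixaban in Japan". SAP 2.1.1 gives the window: "Patients registered in the MDV database from February 26, 2013 to December 31, 2021 will be used", which touches nine calendar years.

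SAP 7.1.2.1 makes by-year estimation the default and then adds "Consecutive calendar years of index dates may be collapsed to build logistic regression model with robustness". It gives no criterion for collapsing and no maximum width. The 26 covariates that follow include age on the index date and age at diagnosis, which are patient ages, but not index year or index date. The list carries no redaction mark.

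SAP 7.1.2.2 sets the balance limit: "If the standardized difference is less than 10%, the covariates are considered balanced". It also allows extreme weights to be recoded, with the 5th and 95th percentiles as the example.

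SAP 7.1.2.5 keeps treatment as the only Cox term "if patient characteristics are well balanced between groups based on standardized difference in components of the PS". Otherwise: "If not balanced, the unbalanced variable will be also included to the model in addition to the index OAC treatment". The only sensitivity analysis in SAP 7.2.3 is the E-value, which concerns unmeasured confounding; index year is measured for every patient.

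**The concern.** In this design year is adjusted for because a separate score is fitted in each year. Once years share a model that has no year term, the score is blind to year within that block. Time then confounds the comparison there whenever apixaban's share and the event rate both change across the block. That partly undoes the stated purpose of the amendment.

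Collapsing is offered for model robustness, so it is most likely where one arm is thin. For apixaban that is probably the years just after launch, when its share probably changes fastest. Both primary hazard ratios would carry the remaining time effect. The Cox rule would not pick it up, because index year is not among the PS components it examines.

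**Working it through.** **Inputs from the documents.** Nine index years, 2013 to 2021 (SAP 2.1.1). The feasibility split in SAP Table 1 is 76,260 apixaban and 62,453 warfarin, so 76,260 / 138,713 = 55.0% apixaban. That count is loose: "no inclusion and exclusion criteria were applied when the number of patients was estimated". The feasibility milestone (28 April 2022) also predates the period change, so the warfarin count may include starts before 2013.

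**Inputs assumed.** Equal numbers per year. Steep apixaban path 10/30/45/55/60/65/70/75/80% (mean 54.4%). Flat path linear from 40% to 70% (mean 55%). Event rates falling or rising 3% to 10% per index year.

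**Formulas.** Let s be a year's apixaban share and z the whole-cohort share. The PS is the block share where years are collapsed and s otherwise. Apixaban weight in a year is proportional to s·z/PS, and warfarin weight to (1−s)(1−z)/(1−PS). The HR factor is the weighted mean of (1+d)^y in apixaban divided by the same mean in warfarin, with y = 0 to 8 and d the yearly change. Under the true model the factor should be 1.

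**One case by hand: steep path, first three years collapsed, d = −5%.**
- Block PS = (10+30+45)/3 = 28.3%.
- Weighted apixaban is spread 10:30:45 over the three years (mean year 1.41). Weighted warfarin is spread 90:70:55 (mean year 0.84).
- Mean relative rate in the block: apixaban (10 + 30×0.95 + 45×0.9025)/85 = 0.9307; warfarin (90 + 70×0.95 + 55×0.9025)/215 = 0.9588.
- Years 4 to 9 are balanced, with mean 0.7571 in both arms.
- Overall factor = (0.9307 + 2×0.7571)/(0.9588 + 2×0.7571) = 0.989.

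**All patterns** (whole-cohort index-year standardized difference, SMD; factors for 3% to 10% per year):

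| Pattern | Path | SMD | Rates falling | Rates rising |
|---|---|---|---|---|
| No collapsing | both | 0.000 | 1.000 | 1.000 |
| First two years | steep | 0.027 | 0.998–0.990 | 1.002–1.005 |
| First two years | flat | 0.003 | 0.9997–0.9987 | 1.0002–1.0006 |
| First three years | steep | 0.076 | 0.994–0.973 | 1.005–1.013 |
| First three years | flat | 0.013 | 0.999–0.995 | 1.001–1.002 |
| Three 3-year blocks | steep | 0.118 | 0.991–0.965 | 1.009–1.025 |
| Three 3-year blocks | flat | 0.041 | 0.997–0.989 | 1.003–1.010 |
| 4 + 5 years | steep | 0.256 | 0.981–0.931 | 1.019–1.058 |
| 4 + 5 years | flat | 0.102 | 0.992–0.975 | 1.008–1.027 |

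**Scale against the plan's precision.** Schoenfeld's formula, 4(1.96+0.84)²/(ln HR)², reproduces SAP Table 2: 113 events at HR 0.59 and 78 at 0.53. SE(log HR) = 2/√113 = 0.188. The largest first-three-years factor, 0.973, would turn 0.59 into 0.574 and 0.53 into 0.516. That is 0.027/0.188 = 0.14 SE at 113 events, or 0.43 SE at an assumed 1,000 events (SE 0.063).

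**Truncation.** In a simulation (450,000 patients, steep path, one normal covariate with log odds ratio 0.5), the by-year default gives an index-year SMD of 0.00 before truncation, about 0.20 after cutting at the 5th/95th percentiles, and 0.07 at the 1st/99th. A collapsed model with a categorical year term behaves the same way.

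**Definition of z.** The zeros above need z to be the whole-cohort proportion. If z were computed within each year, the year imbalance would remain with no collapsing at all: SMD 0.90 on the steep path and 0.40 on the flat one.

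**The case against.** **Collapsing may not happen.** The 138,713 feasibility patients average about 15,400 per year. Even at a 10% share, 2013 would hold about 1,540 apixaban patients, or 59 per covariate, and about 15 per covariate if a quarter were eligible. This stands as a reason to expect little collapsing. It does not close an option that the SAP leaves open and unlimited.

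**The Cox-rule gap is mostly moot for narrow blocks.** The thin-arm reasoning supports only the two patterns that collapse the first years. Both stay below 10%, so the rule would add nothing even if it covered index year. This stands, and it makes the year term in the PS model the more important remedy.

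**The breach with three blocks is fragile.** If records start on 26 February 2013 and 180 clear days are needed, 2013 contributes about 128 days, and the steep-path SMD falls from 0.118 to 0.093. A reader might infer that the plan will breach its own 10% limit unnoticed. The documents do not support that: it takes wide blocks together with assumed uptake.

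**Year might be called a PS component** because scores are fitted by year. The SAP does not list it as one, so at best this is ambiguous.

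**Truncation is a separate, optional step.** That is right. It follows that year imbalance is not confined to collapsed years, and that its size depends on the cutoff chosen.

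**Conclusion.** The gap is real and follows from the text: the SAP permits collapsing without a width limit, has no year term in the collapsed model, and has a Cox rule that does not reach index year. The effect is probably small. For the likeliest patterns (the first two or three years), the hazard ratio moves by about 0.03% to 2.7% with falling event rates and 0.02% to 1.3% with rising ones. The SMD stays below 0.10. It passes 0.10 only with wider blocks: 0.04 to 0.12 for three 3-year blocks and 0.10 to 0.26 for 4 + 5 years.

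All sizes rest on assumed uptake, year sizes and event trends. Two stronger inferences fail. The by-year default does adjust for time, given a whole-cohort z and no truncation. Nor is there a known bias towards apixaban: with its use rising, falling event rates would favour apixaban and rising rates would favour warfarin. A planning hazard ratio of 0.59 or 0.53 would not be overturned in the patterns that collapse only the first years. This is a point to consider, with moderate confidence.

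**What to change.** 1. In SAP 7.1.2.1, include index year as a categorical covariate in every PS model that spans more than one year, and state a maximum number of years that may be collapsed.
2. Add index year to the balance table, assessed after any weight truncation, and name it among the variables covered by the 7.1.2.5 rule.
3. In 7.1.2.2, state that z is the whole-cohort treated proportion.

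The cost is a few model terms and one row in the balance table. Weights become more variable than in a collapsed model without year, but about the same as under the SAP's own default. In the simulation with the first three years collapsed, the weight SD was 0.558 without the year term, 0.736 with it and 0.735 by year. The apixaban effective sample size was 79% of the arm without the term and about 60% under the other two. The year term alone does not protect against truncation, so item 2 is needed as well.

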4.3. OTHER ANALYSIS SET

Not applicable. All eligible patients will be used for the analysis except the pre-designated subanalysis.

Ì		
CCI		

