7.2.3. Sensitivity analysis

E-values will be calculated to assess the extent of unmeasured confounding on findings from primary analyses of effectiveness and safety outcomes. E-value is a measure developed by VanderWeele and Ding (2017) as the minimal strength of association between a hypothetical unmeasured confounder with both the treatment and outcome to explain away the identified association between treatment and the outcome.

PFIZER CONFIDENTIAL

Page 19 of 51

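### The propensity list omits number of chronic medicines, cardiac ablation and cancer, and the Cox fallback cannot adjust for a variable outside that list

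*SAP*

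**What the plan says.** SAP 7.1.2 gives the purpose of the score: "A propensity score will be calculated based on multivariable logistic regressions in order to account for confounding effects". SAP 7.1.2.1 says the models, fitted by calendar year of index date, "incorporate potential predictors of therapy as independent variables in the regression", and then sets out the terms under "The following covariates will be included in the logistic regression". The list shows no redaction. It has 26 terms: two ages, gender, two stroke risk scores, twelve diagnoses, eight drug classes and cardioversion.

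Three factors that appear elsewhere are not in it:

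- **Number of chronically prescribed medicines.** A patient characteristic in Protocol 9.5; SAP 5.4 defines a chronic medicine by a 30-day minimum in the baseline period.
- **Cardiac ablation.** A visible yes/no covariate in SAP 5.4, with codes in SAP 10.3.2.
- **Cancer.** Coded in SAP 10.3.1, and referred to from SAP 10.3.5 as active cancer.

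On balance, SAP 7.1.2.2 says "After the weights are applied, the balance of the baseline covariates will be assessed", with a standardised difference below 10% as the criterion. SAP 7.1.2.5 fits treatment alone in the Cox model "if patient characteristics are well balanced between groups based on standardized difference in components of the PS", and otherwise adds the unbalanced variable. SAP 7.2.3 says "E-values will be calculated to assess the extent of unmeasured confounding on findings from primary analyses of effectiveness and safety outcomes". SAP 6 says "No imputation for missing values will be conducted".

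**The concern.** The balance check covers baseline covariates in general, but the action attached to it is tied to the components of the score. If the medicine count, say, differed by 12% in standardised units after weighting, the SAP would report it and still fit treatment alone. The primary hazard ratios for stroke/SE and major bleeding would carry whatever that imbalance contributes.

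The medicine count and cancer matter most. SAP 2 names polypharmacy and significant comorbidity as marks of the high-risk patients the study is about, and both may plausibly bear on drug choice and on bleeding or stroke at age 80 and over. Eight yes/no drug flags capture a count of all chronic medicines only in part. Cancer has almost no proxy in the list: the liver dysfunction codes include C220 and nothing else from the cancer list.

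The E-value does not fill the gap. It states how strong a confounder would have to be; it does not adjust for one that has been measured.

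**Working it through.** **1. Plan figures used as a scale.** No stated figure depends on the covariate list. The planning hazard ratios in SAP 4.5 are 0.59 (major bleeding) and 0.53 (stroke/SE). They do drive Table 2: 4 × (1.960 + 0.842)² / (ln HR)² gives 113 and 78 events. Dividing by the mean annual rate gives 113 / 0.0184 = 6,141 and 78 / 0.0145 = 5,379 patients, as printed.

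**2. Assumptions.** The documents give no prevalence by arm and no outcome association for these factors, so every input below is assumed, for one omitted factor at a time.

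**3. Binary factor.** Shift = (1 + p_A(HR − 1)) / (1 + p_W(HR − 1)), where p_A and p_W are the weighted prevalences under apixaban and warfarin and HR is the factor's effect on the outcome. Example: 15% v 20% at HR 1.5 gives 1.075 / 1.100 = 0.977. The standardised difference is the absolute difference over √[(p_A(1 − p_A) + p_W(1 − p_W)) / 2].

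| Apixaban v warfarin | Std. difference | Shift, HR 1.5 | Shift, HR 2.0 |
|---|---|---|---|
| 20% v 21% | 0.025 | 0.995 | 0.992 |
| 12% v 15% | 0.088 | 0.986 | 0.974 |
| 3% v 5% | 0.102 | 0.990 | 0.981 |
| 15% v 20% | 0.132 | 0.977 | 0.958 |
| 8% v 12% | 0.134 | 0.981 | 0.964 |
| 40% v 50% | 0.202 | 0.960 | 0.933 |

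Reversing the arms inverts the factor: 20% v 15% gives 1.023 and 1.043.

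**4. Medicine count.** Shift = (HR per SD)^d, with d the standardised difference and HR per SD of 1.2 or 1.3.

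| d | HR per SD 1.2 | HR per SD 1.3 |
|---|---|---|
| 0.03 | 1.005 | 1.008 |
| 0.10 | 1.018 | 1.027 |
| 0.15 | 1.028 | 1.040 |
| 0.20 | 1.037 | 1.054 |

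**5. Reading the tables.** At a standardised difference of about 0.10 to 0.15 the shift is about 2% to 4%, or 1% to 2% for a rare factor. It is under 1% when the factor is nearly balanced. Shifts of 5% to 7% need a difference near 0.20 with the stronger assumed effects. A difference just under the 10% limit (0.088) still gives 1% to 3%. A Cox trigger at 10% would not catch that, which is a reason to put the count in the score itself.

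**6. Effect on results.** A 4% shift either way takes 0.59 to 0.566 or 0.614, and 0.53 to 0.509 or 0.551. An assumed upper confidence limit of 0.97 becomes 0.97 × 1.02 = 0.989 or 0.97 × 1.04 = 1.009.

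**7. Against random error.** Table 1 counts 76,260 and 62,453 patients before any criteria. If 1,000 to 4,000 events were seen (assumed, 1:1, unweighted), the standard error of the log hazard ratio is 2/√events = 0.063 to 0.032. A 2% to 4% shift (0.020 to 0.039 on the log scale) is then about 0.3 to 1.2 standard errors.

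**The case against.** The strongest case against has five parts.

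- **Confounding is not shown.** Nothing visible says that these factors predict the choice of apixaban over warfarin, and SAP 2 names polypharmacy as a feature of a population of interest, not as a confounder. This stands. A reader might infer that the primary hazard ratios are biased, or biased towards apixaban; the documents support neither.
- **Redaction and intended role.** Active cancer, peptic ulcer and alcohol abuse are visible in 10.3.5 under a subgroup heading, and parts of 5.4 and the section after 4.3 are blacked out. Hidden subgroup analyses may use them. That stands, but subgroup analyses would not change the 7.1.2.1 list or the 7.1.2.5 trigger for the overall comparison.
- **Proxies.** Bleeding, liver and gastric secretion inhibitor terms partly cover peptic ulcer and alcohol abuse, which is why these two are secondary. Ablation may be rare after selection: three of its five codes in 10.3.2 also stand in the cardiac surgery list, and cardiac surgery in baseline is an exclusion.
- **The size presupposes imbalance.** The 2% to 4% range assumes that balance fails after weighting on 26 terms. E-values at the planning hazard ratios are 2.78 and 3.18 (1/HR + √[(1/HR)(1/HR − 1)]), above the effects of 1.5 to 2.0 assumed here. This stands, and it limits the severity.
- **The Cox wording.** The clause on adding the unbalanced variable could be read broadly. The preceding sentence ties balance to the score's components, so the broad reading needs to be written in.

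A reader might also infer that body weight, eGFR and creatinine should be treated in the same way. They need a recorded value, SAP 6 rules out imputation, and SAP 4.3 says "All eligible patients will be used for the analysis except the pre-designated subanalysis". Adding them could drop patients from the primary analysis. Diagnosis flags and prescription counts do not have this problem.

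**Conclusion.** The point holds as a gap in the adjustment rules. Factors that the study can derive from codes and prescriptions are outside the propensity list, and the only route to later adjustment is closed to variables outside it. No bias is demonstrated, and its direction cannot be derived from the documents.

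On assumed prevalences and effects, one such factor moves a hazard ratio by about 2% to 4% if its weighted standardised difference is about 10% or more, and by under 1% if existing terms already balance it. That does not overturn effects near 0.59 or 0.53. It could matter for an observed hazard ratio nearer 1, given the large cohort. Severity: low to moderate; a cheap improvement.

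**What to change.** 1. **Amend SAP 7.1.2.5.** A weighted standardised difference of 10% or more in any baseline covariate derived from diagnosis, procedure or prescription codes and defined in both arms should lead to its inclusion in the Cox model, whether or not it is in the score. This leaves out INR and apixaban dose (one arm only) and body weight, eGFR and creatinine (missing values). It covers cardiac ablation without a further propensity term.
2. **Amend SAP 7.1.2.1.** Add the number of chronically prescribed medicines to each calendar-year or collapsed-year propensity model.
3. **Cancer.** Add baseline cancer to the same models, or to a prespecified sensitivity propensity model, after cleaning the 10.3.1 list. Of its 46 D codes, 26 are benign (D10-D36 without D26) and should be removed; the 9 in situ codes (within D00-D09) and 11 uncertain-behaviour codes (within D37-D48) need review. Peptic ulcer and alcohol abuse belong in the sensitivity model only.

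Cost: SAP wording, a short code-list review and a few terms built from data already held. The weights may become slightly more variable and more calendar years may need collapsing, which 7.1.2.1 already allows. The changes should be fixed before outcomes are compared by arm; if that has already happened, report the extended models as sensitivity analyses added afterwards.
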